## 1.2 Schema

#### 1.4 Schedule of Events

Activity	Screening	Preparatory Session (Baseline)	Ketamine Sessions 			Integration Session	Follow-Up 		
			1	2	3		14 Days	30 Days	90 Days
Visit						0	(±3)	(±7)	(±7)
(Window in days)	-60	0							
Informed Consent	X								
Demographics	X								
Medical History	X								
Eligibility Criteria	X								
Registration 	X								
Clinical and Laboratory Assessments									
Vital Signs 	X		X 	X 	X 				
Physical Exam	X								
ECOG Score	X								
ECG	X		ACI						
Adverse event collection 	X	X	X	X	X	X	X		
Concomitant medications	X	X	X	X	X	X	X		
Complete Metabolic Panel	X								
Urine Drug Screen	X								
Pregnancy Test 	X								
Study Intervention									
Evaluation and Screening 			X	X	X				

Activity	Screening	Preparatory Session (Baseline)	Ketamine Sessions 			Integration Session	Follow-Up 		
			1	2	3		14 Days	30 Days	90 Days
Visit						0	(±3)	(±7)	(±7)
(Window in days)	-60	0							
Ketamine Administration 			X	X	X				
Psychotherapy		X	X	X	X	X			
Assessments									
EDS 	X	X	X	X	X		X	X	X
QIDS-SR-16 		X	X	X	X		X	X	X
C-SSRS Baseline/Screening 	X								
C-SSRS Since Last Visit 		X	X	X	X	X	X		
MEQ-30 			X	X	X				
NADA 			X	X	X				
DADDS 		X	X	X	X		X	X	X
FACIT-Sp 		X					X	X	X
Storyline Integrative Assessment 		X					X	X	X

---

 Ketamine will be given during three sessions, 2 to 7 days apart. Questionnaires, with the exception of the MEQ, may be completed up to 1 day prior to the ketamine session.

 Follow-up will be based on time since completion of the integration session.

 To register eligible patients on study, complete a Clinical Trials Office Subject Registration Form and submit to [[contact]](mailto:[contact]).

 Laboratory assessments should be completed within 28 days of enrollment.

 Vital signs include systolic/diastolic blood pressure, heart rate, respiration rate, pulse oximetry and weight.

 Cardiovascular measures during KAP session (blood pressure, O2 sat, heart rate) will be completed within ten minutes prior to session and at 40 min and 2 hours post-administration. Vitals will be reviewed by an on-site MD with ACLS certification. A crash cart and code response team will be available.

 Adverse events and conmeds will be recorded at the time of the session. Subjects may also be contacted by study staff after the session to assess for any additional adverse events or conmed changes.

 Pregnancy test (serum or urine) must be obtained at screening and  $\leq$  8 days prior to ketamine administration for all women of childbearing potential and as clinically indicated while on trial.

 Evaluation and screening to include the items listed in Section 6.1.2.

 Ketamine will be administered according to Section 6.1.3.

 Existential Distress Scale (EDS). See Appendix 2.

 Quick Inventory of Depressive Symptomatology (QIDS-SR-16). See Appendix 3.

 Columbia-Suicide Severity Rating Scale Baseline/Screening (C-SSRS). See Appendix 4.

 Columbia-Suicide Severity Rating Scale since Last Visit (C-SSRS). To be completed at any time during study participation if a subject is rated as of moderate or high risk on the Baseline/Screening C-SSRS. See Appendix 5.

 Mystical Experiences Questionnaire (MEQ-30) should be completed after ketamine administration. See Appendix 8.

 Nondual Awareness Dimensional Assessment. See Appendix 7.

 Death and Dying Distress Scale. See Appendix 9.

 The Functional Assessment of Chronic Illness Therapy. See Appendix 6.

 See Section 3.3.

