#### 2.3.2 To assess the effect that qualitative experiential aspects of the ketamine experience have on subsequent change to depression and existential distress measures using the Mystical Experiences Questionnaire (MEQ-30) and Nondual Awareness Dimensional Assessment (NADA)

Exploratory Endpoint: Correlation between total score on the MEQ-30 and NADA and change in the EDS score at the 2 week primary outcome time point.

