## 7.3 Patient Reported Outcomes

The response to study therapy will be assessed utilizing the Existential Distress Scale (EDS), Quick Inventory of Depressive Symptomatology (QIDS-SR-16), Patient Health, Columbia-Suicide Severity Rating Scale Baseline/Screening and Since Last Visit (C-SSRS), Death

Transcendence Scale (DTS), Functional Assessment of Chronic Illness Therapy - Spiritual Well-Being (FACIT-Sp), , Nondual Awareness Dimensional Assessment (NADA), Mystical Experiences Questionnaire (MEQ-30), Storyline Integrative Assessment, Patient-Reported Experience on Study Therapy, at the time points indicated in the Schedule of Events.

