## Appendix 7: Nondual Awareness Dimensional Assessment (NADA)

### NONDUAL AWARENESS DIMENSIONAL ASSESSMENT – STATE

*Please read each statement and indicate the extent to which you agree with each statement. In other words, how well does the statement describe what you just experienced, just now?*

	Not at all					Very much					
1. I experienced all things seeming to unify into a single whole.	0	1	2	3	4	5	6	7	8	9	10
2. I experienced all sense of self and identity dissolve away.	0	1	2	3	4	5	6	7	8	9	10
3. I felt surrounded and filled with a blissful warmth or energy.	0	1	2	3	4	5	6	7	8	9	10

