## Appendix 8: Mystical Experiences Questionnaire (MEQ-30)

Instructions: Looking back on the entirety of your session, please rate the degree to which at any time during that session you experienced the following phenomena. Answer each question according to your feelings, thoughts, and experiences at the time of the session. In making each of your ratings, use the following scale:

0 – none; not at all

1 – so slight cannot decide

2 – slight

3 – moderate

4 – strong (equivalent in degree to any other strong experience)

5 – extreme (more than any other time in my life and stronger than 4)

---

1. Loss of your usual sense of time.

2. Experience of amazement.

3. Sense that the experience cannot be described adequately in words.

4. Gain of insightful knowledge experienced at an intuitive level.

5. Feeling that you experienced eternity or infinity.

6. Experience of oneness or unity with objects and/or persons perceived in your surroundings.

7. Loss of your usual sense of space.

8. Feelings of tenderness and gentleness.

9. Certainty of encounter with ultimate reality (in the sense of being able to “know” and “see” what is really real at some point during your experience).

10. Feeling that you could not do justice to your experience by describing it in words.

11. Loss of usual awareness of where you were.

12. Feelings of peace and tranquility.

13. Sense of being “outside of” time, beyond past and future.

---

- 14. Freedom from the limitations of your personal self and feeling a unity or bond with what was felt to be greater than your personal self.
- 15. Sense of being at a spiritual height.
- 16. Experience of pure being and pure awareness (beyond the world of sense impressions).
- 17. Experience of ecstasy.
- 18. Experience of the insight that “all is One”.
- 19. Being in a realm with no space boundaries [L1]  
-SEP-
- 20. Experience of oneness in relation to an “inner world” within.
- 21. Sense of reverence.
- 22. Experience of timelessness.
- 23. You are convinced now, as you look back on your experience, that in it you encountered ultimate reality (i.e., that you “knew” and “saw” what was really real).
- 24. Feeling that you experienced something profoundly sacred and holy.
- 25. Awareness of the life or living presence in all things.
- 26. Experience of the fusion of your personal self into a larger whole.
- 27. Sense of awe or awesomeness.
- 28. Experience of unity with ultimate reality.

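### The one-day pre-session questionnaire window exempts the MEQ but not the NADA, so a form meant to measure the ketamine experience may be completed before dosing

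*Combined protocol and SAP*

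**What the plan says.** The Schedule of Events in section 1.4 places both the MEQ-30 and the NADA at ketamine sessions 1, 2 and 3 and nowhere else. Four statements in the plan bear on when the NADA is completed.

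- Footnote 1, attached to the ketamine session columns: "Questionnaires, with the exception of the MEQ, may be completed up to 1 day prior to the ketamine session". The same footnote sets the spacing: "Ketamine will be given during three sessions, 2 to 7 days apart".
- Footnote 15, for the MEQ-30: "Mystical Experiences Questionnaire (MEQ-30) should be completed after ketamine administration".
- Footnote 16, for the NADA, which in full reads: "Nondual Awareness Dimensional Assessment. See Appendix 7". It gives no timing.
- Section 7.3, which says that the patient-reported outcomes are assessed "at the time points indicated in the Schedule of Events". It adds no separate rule for the NADA.

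The scores are used in objective 2.3.2, whose endpoint is: "Correlation between total score on the MEQ-30 and NADA and change in the EDS score at the 2 week primary outcome time point". Section 9.5 specifies Spearman rank coefficients, reported descriptively.

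**The concern.** Objective 2.3.2 asks whether the quality of the ketamine experience is related to later change in distress. Its two predictors therefore have to be measured after the experience. The plan secures this for the MEQ-30 twice, through the exemption in footnote 1 and the instruction in footnote 15. It does neither for the NADA.

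A coordinator who groups the NADA with the EDS, QIDS-SR-16 and DADDS on the day before dosing is acting within the Schedule, and nothing would flag this as a deviation. The resulting score would not measure the intended predictor and would not be comparable with the MEQ-30 score for the same session. Neither the Schedule nor section 9.5 calls for pre-dose and post-dose NADA forms to be separated, so they could be pooled in one coefficient. A session experience that was not rated at the time cannot be collected again later.

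**Working it through.** The plan states no figure on this point, so there is none to reproduce. The check is mainly a comparison of passages.

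**1. Does anything else require a post-dose NADA?** The places that govern its timing or use are footnotes 1, 15 and 16, section 7.3, objective 2.3.2, section 9.5 and Appendix 7. Only the form in Appendix 7 points to completion after the session, and it does so through its wording, not through a scheduling rule.

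**2. What does the form ask?** Appendix 7 is headed as the State version and asks "how well does the statement describe what you just experienced, just now". The MEQ-30 in Appendix 8 has a similar backward-looking frame: "Looking back on the entirety of your session, please rate the degree to which at any time during that session". Both presuppose that the experience has taken place.

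**3. What would a form completed in the window refer to?** Sessions are 2 to 7 days apart, and the window runs from 1 day before the session up to the session.

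- Session 1: no study ketamine has yet been given.
- Sessions 2 and 3: the shortest gap since the previous dose is 2 − 1 = 1 day, and the longest is 7 days. The form could at most refer to the previous session, not the one it is filed under.

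**4. Is there another use for a pre-dose NADA?** No. It is not scheduled at the preparatory visit or at follow-up, and section 9.5 plans no NADA change score.

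**5. How large could the effect be?** The documents give neither the number of patients who would use the window nor the behaviour of pre-dose scores. The following is an illustration in which every input other than the sample size is assumed.

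- n = 12 (the planned enrolment), with one NADA value per patient, k of them pre-dose.
- Post-dose NADA and EDS change are bivariate normal with assumed true Spearman ρ of 0.3, 0.5 or 0.7. The matching Pearson correlation is r = 2·sin(πρ/6); for ρ = 0.5, r = 2·sin(0.2618) = 0.518.
- The k pre-dose values are replaced either by independent draws from the same distribution or by a common floor value, with ties mid-ranked.
- Each entry is the mean sample Spearman coefficient over 20,000 simulated trials.

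| Pre-dose forms (k of 12) | Pre-dose scores | ρ = 0.3 | ρ = 0.5 | ρ = 0.7 |
|---|---|---|---|---|
| 0 | none | 0.28 | 0.46 | 0.65 |
| 3 | independent of outcome | 0.21 | 0.35 | 0.49 |
| 6 | independent of outcome | 0.14 | 0.23 | 0.33 |
| 12 | independent of outcome | 0 | 0 | 0 |
| 3 | all at scale floor | 0.15 | 0.25 | 0.36 |
| 6 | all at scale floor | 0.07 | 0.11 | 0.16 |
| 12 | all at scale floor | not computable (all tied) | not computable | not computable |

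The direction is not fixed. If pre-dose scores themselves have a Pearson correlation of +0.5 or −0.5 with EDS change, a true 0.3 becomes about 0.36 or −0.08 at k = 6.

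**The case against.** The best reply is that the plan, read as a whole, points to a post-dose NADA. The form is part of the protocol, footnote 16 sends the reader to it, its items are in the past tense, and objective 2.3.2 names the ketamine experience as the construct. Footnote 1 only permits early completion. The MEQ-30 sits in the adjacent row with the same session marks and must follow dosing, so staff would naturally hand out the two forms together.

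This has weight. The documents conflict; they do not positively intend a pre-dose NADA, and the number of early forms may be small or zero. But the form's wording does not withdraw an explicit permission in the Schedule. The plan's authors evidently thought the MEQ needed both an exemption and a post-dose instruction, and the same reasoning covers the NADA.

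Two limits on the illustration also stand. First, it uses one NADA value per patient, whereas the Schedule collects three and neither section 2.3.2 nor section 9.5 says which session or summary enters the correlation. Second, sampling noise at n = 12 is large. With no pre-dose forms the sample coefficient has a standard deviation of about 0.28, 0.25 and 0.19 for true values of 0.3, 0.5 and 0.7, so the shift from three independent pre-dose forms is less than one standard deviation in each case. The table shows a systematic shift under stated assumptions. It does not predict what this trial will observe.

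**Conclusion.** The point holds. As written, footnote 1 allows the NADA to be completed before the experience it is meant to rate. This conflicts with Appendix 7 and with the purpose stated in objective 2.3.2. That conclusion rests on the text alone and needs no assumption.

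The size of the effect is unknown. If pre-dose scores are unrelated to outcome, the NADA–EDS correlation is pulled toward zero; under other assumptions it can move either way. The consequence is confined to one of the two predictors in one descriptive exploratory endpoint. The MEQ-30 correlation is protected by footnote 15, and the primary feasibility endpoint, the safety summaries and the EDS prevalence estimate are unaffected. The correction should still be made, because the affected scores cannot be recovered afterwards and section 3.1 says that the study will inform a larger randomised trial.

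**What to change.** Make two edits in section 1.4:

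- In footnote 1, extend the exemption so that it names both the MEQ-30 and the NADA.
- In footnote 16, add that the NADA is to be completed after ketamine administration, matching footnote 15.

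The cost is two footnote changes, with no extra visit, form or analysis. The change concerns questionnaire timing only.

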## 2 OBJECTIVES AND ENDPOINTS

### 2.1 Primary Objective

To assess the feasibility of recruiting, consenting, enrolling, and completing the study intervention for 12 patients.

Primary endpoint: The recruitment, consent, enrollment, and study completion of 12 patients. Study completion defined as participating in at least 2/3 of the 3 KAP sessions.

### 2.2 Secondary Objectives

#### 2.2.1 To assess the safety and tolerability of ketamine-assisted therapy in the study population.

Secondary Endpoint: The frequency of adverse events (AEs) and serious adverse events (SAEs) characterized by type, severity (as defined by the NIH CTCAE, version 5.0), seriousness, duration, and relationship to study treatment.

#### 2.2.2 To determine the prevalence of existential distress in patients with non-operable GI cancers.

Secondary Endpoint: The proportion of screened patients that meet criteria on the Existential Distress Scale (EDS: Single domain  $\geq 3$  or total score  $\geq 6$ ).

### 2.3 Exploratory Objectives

#### 2.3.1 To assess the effect that KAP has on symptoms of existential distress and depression in patients with non-operable GI cancers as measured by the EDS and QIDS-SR-16.

Exploratory Endpoint: Mean change in score on EDS and QIDS-SR-16 from baseline to 2 weeks post completion of intervention.

#### 2.3.2 To assess the effect that qualitative experiential aspects of the ketamine experience have on subsequent change to depression and existential distress measures using the Mystical Experiences Questionnaire (MEQ-30) and Nondual Awareness Dimensional Assessment (NADA)

Exploratory Endpoint: Correlation between total score on the MEQ-30 and NADA and change in the EDS score at the 2 week primary outcome time point.

#### 2.3.3 To assess the effect that KAP has on symptoms of existential distress and depression in patients with non-operable GI cancers as measured by the Spiritual Well-Being (FACIT-Sp)

Exploratory Endpoint: Mean change in score on FACIT-Sp from baseline to Day 30 post completion of intervention.

**2.3.4** To develop an algorithm with Storyline Health technology to rapidly discover the most predictive and information rich components in the assessment of existential distress and its treatment response.

Exploratory Endpoint: Identification of a behavioral phenotype that better predicts a response to ketamine intervention.

**2.3.5** To evaluate the completion rate of questionnaires using the Storyline platform.

Exploratory Endpoint: The percentage of questionnaires completed.

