**Feature Selection:** Storyline AI measures over 20,000 speech, vocal and facial features from the responses for each question and many are correlated or not useful for detecting some phenotypes of interest. Therefore, in this second step, Short Story technology performs a feature selection analysis that uncovers the most useful features for each tested question in an assessment for predicting a particular phenotype or outcome. The major objective is to uncover the best questions and features when the available data has limited sample size and classes are imbalanced. Our approach will involve implementing the qualitative mutual information (QMI) feature selection algorithm previously detailed by others and proven for high dimensional data, including microarray data for tens of thousands of genes (Nagpal and Singh, 2019). The algorithm will provide a score that combines random forest (RF) feature importance scores with mutual information to obtain a QMI value for each feature. QMI is more powerful than random forest (RF) importance or mutual information alone for feature selection, as previously described (Nagpal and Singh, 2018). In brief, RF will be applied to the speech, vocal and facial feature sets separately for each question and the importance scores of each feature will be calculated, as well as mutual information. RF importance scores will be converted to Preference scores and multiplied by the mutual information to define QMI values for each feature. The features will then be ranked by QMI values and features with a  $QMI > 0$  will be retained. The results will return the most useful speech, facial and vocal features for each question. The usefulness of the features is determined from their ability to differentiate the two classes in a study, such as control versus sick patients.

This approach has many advantages, including broad utility with few parameters to tune, applications to diverse data types with few samples and acceptable computational speed. RF importance scores are powerful for ranking correlated features. Mutual information, which determines the amount of information one random variable can provide about another variable, is then incorporated to further help remove irrelevant and redundant features. When accounting for accuracy and computational efficiency, this combined approach outperforms most methods, including filter, wrapper, embedded and hybrid feature selection strategies (Nagpal and Singh, 2019).

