**Question Selection:** The final step of the Short Story algorithm will provide a score that determines the individual questions that should be retained in a new assessment and those that can be eliminated. In this approach, the input is all of the candidate questions and their optimized speech, vocal and facial features revealed from Short Story Score #2. The individual questions and question combinations that show the most value for predicting the classes of interest will then be determined. We will create a simple two-layer neural network that is architected to take Storyline speech, vocal and facial features as inputs to predict the

phenotypic classes of interest. The algorithm will be designed such that questions are tested in all possible pairwise combinations with 5-fold cross validation. The mean accuracy for predicting the target phenotype is determined for each question combination. Each pairwise question combination is then assigned an index. To compute the Short Story score for each question, we multiply the index and the mean classification accuracy for all question pairings in which that question was included in the predictive model. This vector of index\*accuracy values is summed to yield a score and then the scores for all of the candidate questions are min-max scaled to create the final Short Story question ranking score from 0-to-100, where a high score indicates important questions, and a low score indicates questions that can be pruned. The final results will return the ranking for each question and the mean classification accuracy values for each question.

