### **3.3.3 Psychiatric and Psychology Assessment Components:**

This part of the assessment is a 60-minute program broken into six 10-minute assessments of (i) physical symptoms, (ii) mood & emotion, (iii) cognition, (iv) homeostasis (ie. eating, sleeping, activity patterns) (v) social support and (vi) psychological associations. The program was created, in part, with our collaborator, [name] MD PhD (clinical psychiatrist) from a proven set of psychiatric interview questions and methods for DSM-5 diagnoses of depression, bipolar, anxiety, psychosis, neurocognitive disorders (dementia and delirium), suicidality, addiction, trauma and physical health. This interview uses open-ended questions that evaluate RDoC domains and create a caring and natural interview experience that is non-threatening using “normalization”, “reduction of guilt” and “symptom exaggeration” techniques, as well as providing safety, transparency, education and logical flow. Cognition is assessed, in part, using established clinical tests of cognitive functioning, including tests of (i) orientation (date, day of the week, location), (ii) short-term memory, (iii) long-term memory and recall, (iv) semantic fluency, (v) verbal fluency, (vi) working memory, (vii) attention and (viii) self-initiation. In addition, open-ended questions are included that ask for descriptions of (1) concerns about brain functioning, memory, concentration and fatigue, (2) any noticeable changes in memory or thinking, brain fog, headaches, (3) social interactions and perceived support, and (5) a 1-5-minute story about “something that happened to you this week”. The psychological associations assessment uses open-ended descriptions (“What does this make you think of?”) to capture responses to neutral, positive and negative cues, including Eckman faces (neutral, happy, sad, angry, disgust, surprise, contempt), Open Affective Standardized Image Sets (OASIS) and Affective Norms for English Words (ANEW) with valence, arousal or dominance characteristics predictive of mental illness (ie. death, cruelty, trouble, carefree, good, and praise). Finally, the Storyline assessment includes the standard PHQ-2, GAD-2 and PCL-2 questionnaires of clinical depression, anxiety and trauma symptoms as internal controls for clinical symptomology.

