### 9.5 Exploratory Objectives

Exploratory endpoints include 1) the mean change in score on EDS and QIDS-SR-16 from baseline to 2 weeks post completion of intervention; 2) the correlation between total score on the MEQ-30 and NADA and change in the EDS score at the 2 week primary outcome time point;

and 3) the mean change in score on FACIT-Sp from baseline to Day 30 post completion of intervention.

An additional exploratory objective is to develop an algorithm with Storyline Health technology to rapidly discover the most predictive and information rich components in the assessment of burnout and its treatment response. The associated endpoints are 7) the identification of a behavioral phenotype that better predicts a response to ketamine intervention; and 8) the Storyline questionnaire completion rate.

Analysis of the above exploratory endpoints will be descriptive. Continuous variables will be summarized by the minimum, maximum, mean, standard deviation, and 95% confidence interval. The Storyline completion rate and 95% exact binomial confidence interval will be reported. Spearman rank correlation coefficients will be used to summarize the correlation between the total score on the MEQ-30 and NADA and change in the EDS score at the 2-week primary outcome time point.

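### The Storyline endpoint says a phenotype predicts response better, but no reference predictor is planned, so the analysis cannot show that it beats baseline EDS and QIDS-SR-16

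*Combined protocol and SAP*

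**What the plan says.** Section 2.3.4 gives the endpoint as the "Identification of a behavioral phenotype that better predicts a response to ketamine intervention". Section 9.5 lists it again as "the identification of a behavioral phenotype that better predicts a response to ketamine intervention". Neither says what the phenotype should predict better than.

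The method is in 3.3.2. Questions are first filtered by variance. Features are then kept on a score combining mutual information with random-forest importance, and the criterion is class separation: "The usefulness of the features is determined from their ability to differentiate the two classes in a study, such as control versus sick patients". Pairs of questions then enter a small neural network with 5-fold cross-validation: "The mean accuracy for predicting the target phenotype is determined for each question combination". The output is defined as follows: "The final results will return the ranking for each question and the mean classification accuracy values for each question". Section 9.5 adds only this: "Analysis of the above exploratory endpoints will be descriptive".

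Two places come near a comparator. Section 3.3.3 says that "the Storyline assessment includes the standard PHQ-2, GAD-2 and PCL-2 questionnaires of clinical depression, anxiety and trauma symptoms as internal controls" for symptoms, and section 4 speaks of examining psychosocial predictors. Neither is set up as a benchmark for predicting response. The Schedule of Events places EDS and QIDS-SR-16 at the baseline visit and at the 14-day follow-up, so reference predictors are available.

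**The concern.** *Better* is a comparative word, and a comparison needs the performance of at least two predictors. Here only Storyline's performance is computed.

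This matters because of what Storyline measures. Its questions cover mood, emotion and social support, so the speech, vocal and facial features may well track baseline distress. If baseline severity also predicts change in a symptom score, a phenotype that is only another measurement of severity will tend to score above chance. The report could then call it a better predictor although a ten-item questionnaire already in the data does as well.

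Better cross-validation would not cure this, and neither would a clear definition of response, since neither supplies the missing second predictor. The background section says the study is meant to inform a larger randomized trial. An unbenchmarked claim could therefore carry a burdensome video assessment forward without evidence that it adds anything.

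**Working it through.** The plan states no figure for this endpoint, so there is none to reproduce. The check has a textual part and an illustrative part.

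**Text.** Claim: a phenotype predicts response better (2.3.4, 9.5). Quantities computed: variance of each feature, a selection score against the class label, cross-validated accuracy per question pair, and a 0-100 ranking (3.3.2). Quantities needed for the claim: performance of a reference predictor on the same label, and the difference from it. Neither appears in 3.3.2 or 9.5.

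**Illustration.** Inputs from the documents: 12 enrolled patients (9.1) and 5-fold cross-validation (3.3.2). Everything else is assumed:

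- Latent response L = b × EDS + noise, with correlation b = 0.5 or 0.7, split at the median into 6 and 6.
- Storyline score S = r × EDS + noise, with correlation r = 0.5 or 0.7 and no information on L beyond EDS.
- One pre-fixed score, a midpoint classifier, and 5,000 simulated trials per cell.

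The correlation of S with L is then r × b. It runs from 0.5 × 0.5 = 0.25 to 0.7 × 0.7 = 0.49, against 0.5 to 0.7 for EDS itself.

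| b | r | (1) Storyline accuracy > 50% | (2) EDS as good or better, given (1) | Both: (1) × (2) |
|---|---|---|---|---|
| 0.5 | 0.5 | 0.52 | 0.57 | 0.30 |
| 0.5 | 0.7 | 0.60 | 0.59 | 0.35 |
| 0.7 | 0.5 | 0.58 | 0.75 | 0.44 |
| 0.7 | 0.7 | 0.71 | 0.74 | 0.53 |

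Mean accuracy was 0.53-0.61 for Storyline and 0.61-0.71 for EDS.

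Two facts are needed to read column (1) and column (2) correctly:

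- A score of pure noise exceeds 50% in about 44% of trials at this sample size. Re-measured severity therefore adds roughly 52 − 44 = 8 to 71 − 44 = 27 percentage points.
- *As good or better* includes ties, which are common with 12 patients. EDS is strictly better in about 37-52% of the trials in column (1).

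Re-running the simulation gave the same picture within simulation error.

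**Second model, different assumptions.** Here the measure is AUC, response is an above-median fall in EDS, EDS reliability is 0.8, and the coefficient of follow-up on baseline severity is 0.6 (all assumed). The phenotype is a noisy copy of baseline EDS with correlation 0.5 / 0.7 / 0.9.

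- Mean AUC is 0.60 / 0.64 / 0.69 for the phenotype, against 0.71 for EDS.
- The phenotype has AUC above 0.5 in 70% / 78% / 86% of trials.
- In 48% / 52% / 54% of all trials it does so while EDS equals or beats it. At correlation 0.7, moving the coefficient from 0.4 to 0.8 moves this share from 59% to 44%.
- The phenotype still exceeds EDS by luck in 24% / 29% / 34% of trials, so a bare ranking of the two would not be enough.

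**The case against.** The strongest reply is that the plan makes no such claim as a conclusion. A reader might infer that any accuracy above chance would count as meeting the endpoint. The documents do not support that: they set no accuracy threshold and no decision rule, and they call both the study and this analysis descriptive. This part of the reply stands.

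Second, *better* may be internal. The objective above the endpoint is to find the most informative components, and 3.3.2 ranks questions and question pairs against one another. This reading is possible and cannot be excluded. It does not remove the problem, because the endpoint's words do not say so and a reader of the results would not know.

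Third, the simulation builds in its direction: a noisy copy of EDS must lose to EDS on average. That is correct. A reader might also take the 52-71% as the effect of re-measured severity, but most of it is what 12 patients give by chance. The figures show what the plan could not detect; they are not evidence that EDS does predict as well. They also leave out the planned selection ("Storyline AI measures over 20,000 speech, vocal and facial features from the responses for each question") and the narrowing of baseline EDS by the eligibility cut-off.

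Fourth, no response class is defined anywhere, and very many features on 12 patients is the larger weakness of this endpoint. Both are true. The first has to be settled before any comparison can be run.

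Fifth, a strict rule that the interval must exclude zero would be out of scale for a 12-patient pilot. In an illustrative check, a phenotype with real added information (mean accuracy 0.74-0.85 against 0.54-0.62 for EDS) passed such a rule in only about 14-41% of trials. This stands too, and argues for descriptive reporting of the difference and restrained wording.

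**Conclusion.** The point holds on the text: a comparative endpoint is paired with an analysis that evaluates one predictor only. Followed as written, the plan cannot support the statement that a Storyline phenotype predicts response better than baseline EDS or QIDS-SR-16.

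The size is illustrative and rests on the assumed correlations of 0.5-0.7 and a phenotype with nothing beyond EDS. Under those assumptions Storyline looks better than a coin toss while EDS does as well or better in about 30-53% of all trials. Whether EDS really predicts response in these patients is unknown.

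The consequence is limited to how one exploratory result may be worded. It is an optional improvement: study success is defined by completion, and the primary, safety and prevalence analyses do not depend on it.

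**What to change.** In 9.5:

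- State the response label once: the scale, the time point, and how change is turned into classes. The same paragraph names burnout as the target where 2.3.4 names existential distress; reconcile the two at the same time.
- Fit a reference model on baseline EDS and QIDS-SR-16 with the same label and the same folds as the Storyline model.
- Report the paired out-of-fold difference in performance (Storyline minus reference) descriptively, with an interval resampled by patient.

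In 2.3.4 and 9.5, replace *better predicts* with *is associated with* unless that comparison supports *better*. If only a ranking among Storyline questions was meant, say so.

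The cost is one extra model on data already collected and a few lines of text. With 12 patients each test fold holds two or three people, so the difference will be imprecise and *better* will probably not be supported. Changing the wording alone is the minimum, and it needs no further analysis.
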